4. STUDY DESIGN

4.1. Overall Design

GRAVITAS-309 is a 2-part, multicenter Phase 2/3 study that will assess the efficacy and safety of itacitinib in combination with corticosteroids as first-line treatment for moderate or severe chronic GVHD.

4.1.1. Part 1

Part 1 is a run-in that will employ a randomized, open-label, parallel-cohort design with the primary objective to assess the safety and tolerability of itacitinib in combination with corticosteroids in order to identify the appropriate dose of itacitinib in combination with corticosteroids as initial treatment for moderate or severe cGVHD. A total of 20 participants with moderate or severe cGVHD will be randomized 1:1 to itacitinib 200 mg QD plus corticosteroids or 300 mg QD plus corticosteroids. Itacitinib treatment will continue until treatment failure (cGVHD progression, death, or initiation of new systemic cGVHD therapy), unacceptable toxicity, or withdrawal of consent. Participants will remain on study for a total of 37 months, including study treatment (up to 36 months), safety follow-up (30 days after EOT), and post-treatment GVHD follow-up (up to 24 months from Day 1), unless death or withdrawal of consent occurs earlier.

Chronic GVHD staging and grading will be assessed using NIH consensus guidelines (Lee et al 2015, Jagasia et al 2015); safety and tolerability will be assessed as per NCI CTCAE v4.03.

An analysis to determine the dose for further study will be performed once the 20th participant completes 28 days of study treatment. An external DMC will review data from this analysis and provide a recommendation on an appropriate dose for Part 2.

4.1.2. Part 1 Expansion

Part 1 expansion is a Phase 2 with an initial safety run-in that will employ a randomized, open-label, parallel-cohort design with the primary objective to assess the safety and preliminary efficacy of itacitinib in combination with corticosteroids compared with corticosteroids monotherapy and identify the appropriate dosing/schedule of itacitinib in combination with corticosteroids as initial treatment for cGVHD for Part 2. A total of up to 140 participants (35 per treatment group) with moderate or severe cGVHD will be randomized 1:1 to 1 of 4 treatment groups (Table 8), specifically: itacitinib 300 mg QD plus corticosteroids (Treatment Group A), itacitinib 400 mg QD plus corticosteroids (Treatment Group B), itacitinib 300 mg BID plus corticosteroids (Treatment Group C) or corticosteroids monotherapy (Treatment Group D).

Table 8: Treatment Groups and Dose Levels and Schedules

Treatment Group	Dose Level and Schedule
A	Itacitinib 300 mg QD plus corticosteroids
В	Itacitinib 400 mg QD plus corticosteroids
С	Itacitinib 300 mg BID plus corticosteroids; may be decreased to 200 mg BID if a boundary is reached during safety run. This treatment group was discontinued due to concern of a potential increase in relapse rate. Participants in this treatment group who were ongoing were allowed to reduce to 400 mg QD plus corticosteroids.
D	Corticosteroids monotherapy.

Randomization will be stratified by cGVHD risk status (moderate vs severe). Treatment groups B and C will have an initial safety run-in of 10 participants to determine safety and tolerability of the dose before expanding (see definition of DLT in Section 6.1.1.3). Participants enrolled in the safety run-in will be monitored continuously using the Bayesian approach (Section 10.4.1.1). Treatment Group C was discontinued as of Amendment 8 and participants in that treatment group who were ongoing were allowed to reduce to 400 mg QD plus corticosteroids.

Itacitinib treatment will continue until treatment failure (cGVHD progression, death, or initiation of new systemic cGVHD therapy), unacceptable toxicity, or withdrawal of consent. Participants will remain on study for a total of 37 months, including study treatment (up to 36 months), safety follow-up (30 days after EOT), and post-treatment GVHD follow-up (up to 24 months from Day 1), unless death or withdrawal of consent occurs earlier.

Chronic GVHD staging and grading will be assessed using NIH consensus guidelines (Lee et al 2015, Jagasia et al 2015); safety and tolerability will be assessed as per NCI CTCAE v4.03.

Telephone conferences with study investigators will be scheduled by the sponsor in order to review cohort-specific data and overall safety data, to adjudicate individual high-grade AEs as potentially dose-limiting, and to guide other major study decisions.

An analysis to determine the dose and schedule for Part 2 will be performed once the last participant completes at least 3 months of study treatment (see Section 6.1.1.4). An external DMC will review the data from this analysis and provide a recommendation on an appropriate dose for Part 2.

Participants who are randomized to the steroids single-agent cohort may be crossed over once the appropriate dosing/schedule for itacitinib for Part 1 was determined provided the participant completed 6 months of treatment with corticosteroids alone.

4.1.3. Part 2

Part 2 will employ a randomized, double-blind, placebo-controlled design in order to assess the efficacy of itacitinib in combination with corticosteroids using the dose selected in Part 1 expansion. Randomization will be stratified by cGVHD risk status (moderate vs severe). Participants randomized to the placebo group will be permitted to cross over to the experimental group after completion of the primary analysis as appropriate. Participants will remain on study for a total of 37 months, including the treatment period, safety follow-up, and post-treatment

GVHD follow-up, unless confirmed GVHD progression, start of a new GVHD therapy, or relapse/recurrence of underlying hematologic disease occurs earlier.

GVHD staging and grading will be assessed using NIH consensus guidelines (Lee et al 2015, Jagasia et al 2015); safety and tolerability will be assessed as per NCI CTCAE v4.03.

An interim analysis for futility will be performed once 70 participants have completed the Day 180 visit; the final analysis will be performed once all participants have completed the Day 180 visit.

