10.4.3. Safety Analyses

Safety analyses will be conducted for the safety population. Adverse events will be coded by the MedDRA dictionary, and TEAEs (ie, AEs reported for the first time or worsening of a pre-existing event after first dose of study drug/treatment) will be tabulated by preferred term and system organ class for all events, related events, and events of Grade 3 or higher. Quantitative safety variables and their changes from baseline (laboratory, vital signs, etc) will be summarized with descriptive statistics. Clinically notable abnormal values will be flagged and tabulated based on predefined criteria.

Clinical laboratory data will be analyzed using summary statistics; no formal treatment group comparisons are planned. In addition, distributions of key laboratory parameters may be plotted over time; these values will also be classified into CTCAE v4.03 toxicity grades and tabulated. Descriptive statistics and mean change from baseline will be determined for vital signs at each assessment time. Vital sign results will be reviewed for clinically notable abnormalities.

Measures of exposure (eg, days of exposure, dose intensity, etc) of study drug and reference therapy will be summarized by means of summary statistics.

In order to accommodate the changes proposed in Protocol Amendment 8 that resulted in discontinuation of Treatment Group C (300 mg BID) and subsequent dose reduction of on-going participants in Treatment Group C to 400 mg QD, safety tables (specifically AEs) will be presented for the 300 mg BID group with participants who are subject to dose reduction and censored at the date of switching to the lower dose (400 mg QD). In addition, an overall summary including both dose groups (participants included before and after the dose reduction) will also be presented.

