5.3. Analysis Populations

The populations that will be included in study-related analyses are described in [Table 4](#).

Table 4: Populations for Analysis

| Population | Description |
|---------------|---|
| ITT | All randomized participants |
| Safety | All enrolled/randomized participants who received at least 1 dose of study drug and/or reference therapy. Treatment groups for this population will be determined according to the actual treatment the participant received regardless of assigned study drug treatment. |
| Safety run-in | All participants enrolled in the safety run-in portion of the study who received at least 1 dose of study drug and/or reference therapy. Treatment groups for this population will be determined according to the treatment assignment on Day 1 regardless of the actual study drug the participant might take during their continued participation in the study. |
| PK evaluable | All participants who received at least 1 dose of study drug and/or reference therapy and provided at least 1 postdose plasma sample (1 PK measurement). The study pharmacokineticist will review data listings of study drug administration and sample records to identify participants to be excluded from analyses of PK data. |

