7.3. Analyses of the Secondary Efficacy Parameters

7.3.1. Response Rate

Response rate at 3, 6, and 12 months (Days 90, 180, and 365) is defined as the proportion of participants who achieved a response (CR or PR) at each of these timepoints based on an ITT population.

A participant will not be considered a responder for the analysis of ORR at 3, 6, and 12 months if any of the following events occurred at or prior to the response assessment at the predefined timepoint:

- cGVHD progression per NIH response criteria or initiation of a new systemic therapy for cGVHD

- Evidence of progression of the underlying hematologic disease
- Withdrawal from the study
- Death
- Response assessment missing (not performed) at the predefined timepoint

The proportion of responders will be estimated with 95% CIs. Confidence intervals will be calculated based on the exact method for binomial distributions. Summary statistics will be provided.

Additional analyses may be performed based on evaluable subsets. An evaluable population will also be considered with participants who have completed 3, 6, or 12 months of follow-up as of the cutoff date or discontinued earlier because of new cGVHD progression. Presentations of ORR at Month 3 and Month 6 will include a footnote explaining what "evaluable" means (ie, participants who had at least 3 or 6 months of follow-up as of the cutoff date or discontinued earlier).

Summary statistics and 95% CI will be provided by cohort. The primary comparisons in Part 1 expansion will involve only the 2 itacitinib groups (Treatment Groups A and B) and the corticosteroids-only group (Treatment Group D) as a result of Protocol Amendment 8, in which Treatment Group C (300 mg BID + corticosteroids) was discontinued. Data from Treatment Group C will be presented only as summary statistics and will not be subjected to any statistical comparison.

Pairwise Cochran-Mantel-Haenszel tests will be conducted for Month 6 response rate for each of the 2 itacitinib groups (Treatment Groups A and B) and the corticosteroids-only group (Treatment Group D) as an exploratory analysis.

The secondary endpoints discussed below will be summarized by Treatment Groups A, B, and D using the ITT population for efficacy-related endpoints and all groups for safety-related endpoints.

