9.1. General Considerations

All safety analyses will be conducted for the safety population and summarized by treatment group. Summary tables may be replaced with listings when appropriate. For instance, an AE frequency table may be replaced with a listing if it only contains a few unique PTs reported on relatively few participants.

In order to accommodate the changes proposed in Protocol Amendment 8 that resulted in discontinuation of Treatment Group C (300 mg BID) and subsequent dose reduction of ongoing participants in Treatment Group C to 400 mg QD, safety tables (specifically AEs) will be presented for the 300 mg BID group with participants who are subject to dose reduction and censored at the date of switching to the lower dose (400 mg QD). An overall summary including both dose groups (participants included before and after the dose reduction) will also be presented.

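### The SAP has no cut-off or attribution rule for Group D after crossover, so adverse events, relapses and first responses on itacitinib can enter the corticosteroids-only column after Month 6

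*Protocol*

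**What the plan says.** **Crossover.** Protocol 4.1.2 states that "Participants who are randomized to the steroids single-agent cohort may be crossed over" once the itacitinib dosing or schedule has been determined, "provided the participant completed 6 months of treatment with corticosteroids alone". The dose analysis takes place "once the last participant completes at least 3 months of study treatment".

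**Switch rule.** One exists, for Group C. Protocol 10.4.3 says "safety tables (specifically AEs) will be presented for the 300 mg BID group", and SAP 9.1 repeats this, with participants who reduce their dose "censored at the date of switching to the lower dose (400 mg QD"). Both add an overall summary covering the time before and after the switch. Neither document has a matching rule for Group D.

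**Grouping.** In SAP 5.3, safety-population groups are "determined according to the actual treatment the participant received regardless of assigned study drug treatment". SAP 7.1 and Appendix A run Part 1 expansion efficacy on that population, while SAP 7.3.1 and Protocol 10.4.2.2 name the ITT population.

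**Time windows.**
- Treatment-emergent AEs run until 30 days after the last dose of study drug (SAP 9.2.1).
- Best overall response covers the whole study (SAP 7.3.4).
- Relapse rate and time to relapse have no cut at a change of treatment (SAP 7.3.7, 7.3.8).
- "Response rate at 3, 6, and 12 months (Days 90, 180, and 365") excludes as responders those with "cGVHD progression per NIH response criteria or initiation of a new systemic therapy for cGVHD" at or before the assessment (SAP 7.3.1).
- Duration of response ends, as an event, at new systemic cGVHD therapy (SAP 7.3.3).

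**The concern.** The sponsor recognised that a change of regimen distorts AE tables by arm and wrote a rule for the arm that moved from one itacitinib dose to another. The arm that may move from no itacitinib to itacitinib has no rule.

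This matters for three reasons. AE incidence and severity across cohorts is the primary endpoint of the Part 1 expansion. Group D is its only itacitinib-free comparator. Relapse is the signal that closed Group C: at the July 2021 cutoff there were 4 relapses in C (n = 24), 1 in A (n = 32), 1 in B (n = 25) and 0 in D (n = 26). If itacitinib raises the risk of an event, counting post-crossover events in Group D shrinks the contrast that the arm was added to show.

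The exposure involved need not be small. Treatment may last up to 36 months, and the Appendix A tables are for the Clinical Study Report, which follows the end of the study. A participant who crosses over at Month 6 could contribute up to 36 − 6 = 30 months on itacitinib, if the 36-month limit runs from Day 1.

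**Working it through.** There is no stated figure to reproduce, because the Part 1 expansion has no formal test and the documents give no expected crossover count. The check sets the rules side by side and then sizes the effect on assumed counts.

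**Step 1. What happens to each output after a Group D participant starts itacitinib?**

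| Output | Rule as written | After crossover |
|---|---|---|
| Month 3 and 6 response | Fixed timepoints | Not affected: crossover needs 6 months of corticosteroids alone |
| Dose decision | Last participant at 3 months or more | Not affected: the decision is what opens crossover |
| Treatment-emergent AEs | To 30 days after last dose | No cut; attribution undefined |
| Best overall response | Whole study | A first response on itacitinib can count for D |
| Relapse rate, time to relapse | From randomization, no cut | Counted in D if analysed as randomized |
| NRM, OS | From randomization, no cut | Counted in D if analysed as randomized |
| Month 12 response | Non-response after new systemic therapy | Probably non-response; not stated |
| Duration of response | Event at new systemic therapy | Probably an event; not stated |

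Best overall response differs from time to response, which SAP 7.3.2 limits to responses before new therapy.

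**Step 2. AEs.** Inputs are the Part 1 thrombocytopenia/platelet count decrease rate of 9/21 = 42.9% (Protocol 2.3.2.1), 35 participants planned in Group D, and an assumed number k crossing over. Cases added = k × 9/21; points added = cases / 35.
- k = 5: 2.1 cases, 6.1 points
- k = 10: 4.3 cases, 12.2 points
- k = 15: 6.4 cases, 18.4 points

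At that rate these are upper values, since they assume that no crossover participant already had the event counted on corticosteroids alone.

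**Step 3. Relapse.** Each post-crossover relapse adds 1/35 = 2.9 points. With exact binomial intervals, the method named in SAP 7.3.7:
- 0/35 = 0% (0 to 10.0)
- 1/35 = 2.9% (0.1 to 14.9)
- 2/35 = 5.7% (0.7 to 19.2)

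**Step 4. Month 12 response, if the rule stays unstated.** Assume 20 of 35 in Group D are in response at Month 12. Ignoring crossover gives 20/35 = 57.1%. If crossover counts as new systemic therapy and 2, 5 or 10 of those responders had crossed over, the rate is 18/35 = 51.4%, 15/35 = 42.9% or 10/35 = 28.6%. The two readings differ by 5.7, 14.3 or 28.6 points. Only crossovers before the Month 12 assessment matter here.

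**The case against.** The strongest reply is that existing rules already cover much of this and that what remains is late, descriptive data. Several parts of it stand.

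- **Month 12 response and duration of response.** A reader might infer that itacitinib-era responses at Month 12 are credited to Group D. The documents do not support that. SAP 7.1 includes the start of a new anti-GVHD therapy in its definition for all efficacy analyses, and itacitinib first given after 6 months of corticosteroids alone fits it on a plain reading. The result would be non-response at Month 12 and a duration-of-response event, which moves Group D down. Someone could still argue that protocol-permitted crossover drug is study treatment rather than new therapy, so the SAP should settle it.
- **AEs.** It is too firm to say that post-crossover AEs will be counted in Group D. The window does not stop at crossover, but assignment of someone who received both regimens is undefined.
- **The Group C rule.** It covers AE tables only and is no precedent for censoring relapse, NRM or OS. Following randomized groups through crossover is a legitimate choice for those endpoints. Participants who reach 6 months on corticosteroids alone are selected, so censoring them could be informative.
- **Relapse comparison.** A reader might say that one post-crossover relapse would bring Group D level with Group A. That sets a future count in D against the July 2021 count in A, which continues to accrue follow-up.

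The absence of formal tests does not answer the point, because the descriptive tables by arm are what the expansion will report.

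**Conclusion.** The gap is real and should be closed, within limits. The SAP omits a treatment change that the protocol permits in its only itacitinib-free arm. As a result AE attribution is undefined, and best overall response and the relapse summaries run through crossover without comment. For Month 12 response and duration of response, a rule that probably applies needs one confirming sentence.

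The effect is confined to data after Month 6. A reader might infer that dose selection for Part 2 is compromised; it is not, because the data behind that decision precede any crossover.

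The sizes in the working are illustrations. They rest on assumed crossover counts and, for thrombocytopenia, on a rate from 21 participants given 200 mg or 300 mg QD in Part 1. No single value, including the 12-point figure, is an estimate of the bias to be expected.

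**What to change.** 1. **SAP 9.1.** Extend the Group C AE rule to Group D: censor the Group D AE tables at the first itacitinib dose, tabulate post-crossover AEs separately, and keep an overall summary. SAP 6.4 already derives the start of itacitinib from the dosing record, which can supply the cut date.
2. **SAP 7.1.** State that crossover to itacitinib is initiation of new systemic therapy. It then gives Month 12 non-response, is a duration-of-response event, and ends the window for best overall response.
3. **SAP 7.3.5 to 7.3.8.** Keep relapse, NRM and OS by randomized group as the main analysis and say so, since SAP 7.1 and Appendix A point to a population grouped by actual treatment. Add a supportive presentation of Group D relapse up to crossover.

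The cost is a few SAP lines, extra table columns and shorter Group D AE follow-up in the main table. Item 2 also lowers the Group D Month 12 rate by 1/35 = 2.9 points for each participant who crosses over while in response, so the number crossing over should be shown beside that rate.

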4.2. Overall Study Duration

The study begins when the first participant signs the ICF. A participant is considered to have completed the study once all periods of the study are finished or consent is withdrawn. It is estimated that an individual participant may participate for as long as 38 months.

The primary analysis for Part 1 will occur once the last evaluable participant completes 28 days of treatment or experiences a DLT. In Part 1 expansion, an analysis to determine the dose and schedule for Part 2 will be performed once the last participant completes at least 3 months of study treatment. Participants who are still on treatment at the time of this analysis will continue to receive study treatment until treatment withdrawal criteria are met (Section 7.1.1). In Part 2, the primary analysis will occur once the last participant enrolled in the study completes all required Day 180 assessments. At the time of the primary analysis, any remaining participants may continue to receive study treatment and be assessed as per Protocol for a maximum of 36 months or until treatment withdrawal/study withdrawal criteria are met. Participants who are randomized to placebo may also be crossed over at the time of the primary analysis as appropriate. The study will end once all randomized participants have reached Month 36 or discontinued the study early due to any reason; at this time, the clinical study report will be generated.

4.3. Study Termination

The investigator retains the right to terminate study participation at any time, according to the terms specified in the study contract. The investigator is to notify the IRB/IEC in writing of the study's completion or early termination, send a copy of the notification to the sponsor or sponsor's designee, and retain 1 copy for the site study regulatory file.

The sponsor may terminate the study electively, if required by regulatory decision or upon advice of the DMC. If the study is terminated prematurely, the sponsor will notify the investigators, the IRBs and IECs, and regulatory bodies of the decision and reason for termination of the study.

5. STUDY POPULATION

Deviations from eligibility criteria are not allowed when enrolling a participant into the study, because they can potentially jeopardize the scientific integrity of the study, regulatory acceptability, and/or participant safety. Therefore, adherence to the criteria as specified in the Protocol is essential. Prospective approval of Protocol deviations to recruitment and enrollment criteria, also known as Protocol waivers or exemptions, are not permitted.

